D5.2 EHR variable construction: EHR measures are listed in Table 5. Monthly EHR sums will be averaged by quarter and by year. If categorical variables change over an aggregated time point, the most consistent designation over the analyzed epoch will be used.

Health Services Utilization
Outpatient Visits (any service)
Outpatient Visits (MH service)
Emergency or Urgent Care Visits
Inpatient MH
Inpatient (any service)
Pharmaceutical Utilization
Antidepressant
Antipsychotic
Mood Stabilizer
Anxiolytics
Other medications (non-psychiatric)
Change in Pharmaceutical
Antidepressant
Antipsychotic
Mood Stabilizer
Anxiolytics
Other medications (non-psychiatric)
Mental Health (Current and Lifetime)
Depression
Bipolar disorder
Schizophrenia or schizoaffective disorder
Generalized Anxiety Disorder
Posttraumatic Stress Disorder
Specific Phobia
Panic Disorder
Social Phobia
Personality Disorder
ADHD
SUD
Gambling Disorder
Eating Disorders
Suicidality

Table 5. EHR data extracted at baseline and follow-

E. DATA ANALYSIS

E1. Design and Sample Size

This is a single-site, two-arm RCT with individual participant urn randomization. We propose to randomize 130 Veterans. Approximately 65 will be randomized to active TMS+BCBT and 65 participants will be randomized to sham TMS+BCBT. Recruitment for the intervention will cease once randomization goals are met (i.e. n= ~65 Veterans per condition). Additionally, we will be enrolling 60 Veterans, who will be matched on age (within 5 years), primary psychiatric diagnosis, and sex, for a total of 190 Veterans to be enrolled. A subsample of these veterans (120 in total; one group (n=30) with suicide ideation and another group (n=30) with suicide attempts; and controls (n=60) will be used in the analyses of brain-based biomarkers for suicidality. Veterans will be assessed at the study timepoints outlined in C3. Assessments.

E1.1 Overall Analytic Approach across Aims

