Preliminary analyses will include descriptive statistics to examine the distributional and psychometric properties of the variables (e.g., normality, internal consistency). Variables will be transformed to achieve normality if necessary. We will also examine post-inclusion attrition by comparing study completers to dropouts on sociodemographic, baseline, and length of admission data to determine if they differ systematically. Preliminary analyses may also include analyses of adverse events, progress of recruitment and retention, and quality markers as the study progresses. In keeping with the intention to treat principle, missing data will be handled with multiple imputations (m=20) with assumptions checked with sensitivity analyses [43,44] [32]. Our main analysis will not adjust for covariates other than baseline value of the outcome and design factors (balancing factors used in the urn randomization procedure) under the assumption that randomization produced groups balanced on measured and unmeasured confounders. Additionally, the data from this study across all Aims will be combined with data from subjects who completed neuroimaging procedures in PVAMC IRB protocol #2018-051.

Data from this study, across all Aims, will also be combined with data from subjects who completed procedures for PVAMC IRB protocol #IRB-2020-008. Data from this study related to recorded interviews, de-identified with the exception of assessment dates, will also be shared with the PVAMC research study “Longitudinal Assessment of the Sleep-Suicide Link in Veterans Discharged from Inpatient Psychiatric Care” (IRB-2020-008), for training of staff and inter-rater reliability analysis (i.e., to calculate agreement across interviewers and to make final decisions on ratings).

E2. Aim 1 Analytical Plan (Analyses Related to Treatment)

The data from this study for Aim 1 may be combined with data from subjects who completed neuroimaging procedures in PVAMC IRB protocol #2018-051. Data from this study, for Aim 1 may also be combined with data from subjects who completed procedures for PVAMC IRB protocol #IRB-2020-008.

E2.1 Interim analysis and early stopping of treatment

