E2.2.1 Statistical power and sample size for our primary outcome: With 65 persons per group, Lehr's equation [73] instructs that minimum detectable standardized mean difference effect size difference (d) between treatment groups at the baseline assessment is $\text{sqrt}(16/n)$, where n is the per-group sample size, or 0.50 standard deviation units, a medium effect size in Cohen's effect size taxonomy [74]. Given the ANCOVA design, we will be able to detect a smaller effect depending upon the magnitude of the pre-post correlation (r) of the suicidal behavior composite outcome $\{d = \text{sqrt}([16(1-r^2)]/n)\}$, which under the assumption of a moderate correlation (r = .2) the minimum detectable effect size is $d = .47$. These are medium or typical effect size magnitudes [75] and are likely to describe effects of minimal clinical significance or practical importance. Of note, these are also comparable with prior TMS studies [64,65] who described effect sizes of .5-.52, and more recent studies indicating larger (d=.9) effect sizes of TMS used with medications [76]. While we recognize these are effect sizes for depressive symptoms, in our pilot work we found reduction in depressive and suicide-related symptoms to be highly correlated. For our secondary outcome, we used simulations to determine the minimum detectable difference. If we assume that 21% of the sample will experience a suicide attempt over 12 months follow-up, if the cumulative risk of suicide attempt is 4.5% over 12 months in the TMS+BCBT group (hazard ratio = 0.19) we

will have 81.1% power to detect such an effect using a type-I error rate of 5% in a Cox proportional hazards model framework.

E2.3 Secondary hypotheses

For this aim we hypothesize, compared to sham TMS+BCBT, Veterans who receive active TMS+BCBT will have superior improvements in psychosocial functioning and fewer psychiatric hospitalizations/crisis visits during the follow-up period. The outcomes for this aim are a)

WHODAS score b) number of psychiatric hospitalizations/crisis visits c) reduced suicide ideation as measured by the C-SSRS. The analysis for the psychosocial functioning outcome, (a), and the suicidal ideation severity score from the C-SSRS, (c), will be a repeated measures ANCOVA, as with the primary hypothesis, using a generalized linear mixed effect model. For part (b), the outcome will be a count variable, for which we will use negative binomial regression.

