E2.4.1 Statistical power and sample size considerations: As we view tertiary analyses as exploratory and hypothesis generating, we do not present a priori specified sample size or minimum detectable effect size statistics. We have no doubt that we may be underpowered to detect all but large moderation effects. Our inferences will be made cautiously and be guided

by confidence intervals obtained by bootstrap resampling of the observed data.

E3. Aim 2 Analytical Plan (Analyses Related to Cognition and Neuroimaging)

All de-identified data from this study for Aim 2 will be combined with data from subjects who completed neuroimaging procedures in PVAMC IRB protocol #2018-051.

E3.1 Evaluate the relationship between STBs and reward circuits involved in decision-making in Veterans.

Hypothesis: Neural and behavioral correlates of decision-making will differentiate Veterans with STBs from those without STBs.

Rationale: Suicidality is associated with maladaptive decision-making. Neuroimaging in non-Veterans has shown that STBs are accompanied by functional and anatomical differences in the striatal-to-VMPFC reward circuit implicated in decision-making. It is unknown if these potential neurocognitive markers of suicide generalize to Veterans.

Between-group contrasts of decision-making, structural MRI, and functional MRI will be used to test our hypothesis.

E5.1 Participant groups: The STB group will be comprised of Veterans hospitalized for suicide attempt (up to n=30) or suicidal ideation (up to n=30). The diagnosis matched control group is comprised of Veterans (up to n=60) without current STBs. Per power estimations computed with G Power software⁴², 85% power to detect a medium-sized effect of group (0.4) in an ANCOVA model with three groups and two covariates is afforded by a total sample size of 72, or n=24 participants per group. Our enrollment targets exceed this estimate to account for loss of participants that are unable to complete all aspects of the study.

Data sources: Decision-making tasks include the scanned reward expectancy task (card guessing), and the un-scanned Iowa Gambling and Monetary Choice (Delay Discounting) tasks. Structural MRI and diffusion MRI data. FMRI data used in Aim 1 analyses will come from either the card guessing reward task or resting state functional MRI runs.

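### The detectable effects in E2.2.1 do not follow from its own inputs: .47 recomputes to 0.49 with no dropout, and neither .50 nor .47 allows for the loss to follow-up that the plan foresees

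*Combined protocol and SAP*

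**What the plan says.** E1 fixes the sample: "We propose to randomize 130 Veterans". It continues: "Approximately 65 will be randomized to active TMS+BCBT and 65 participants will be randomized to sham TMS+BCBT". There is no over-recruitment for the treatment aim: "Recruitment for the intervention will cease once randomization goals are met".

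E2.2.1 takes the same number, "With 65 persons per group", and applies Lehr's rule, d = sqrt(16/n), to obtain 0.50. It attaches that figure to a difference "between treatment groups at the baseline assessment". It then gives the ANCOVA form, d = sqrt(16(1 − r²)/n), and reports .47 for r = .2. For support it compares these with effects of .5 to .52 in earlier TMS trials.

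The plan foresees loss in the treatment aim. E1.1 says "We will also examine post-inclusion attrition by comparing study completers to dropouts" and specifies multiple imputation with m = 20. D4.4.3 covers discontinuation and loss to follow-up, and the follow-up section (the second D4.5) pays participants to limit attrition. No rate is given.

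The imaging aim is treated differently. E3.1 needs 72 participants, plans up to 120, and explains: "Our enrollment targets exceed this estimate to account for loss of participants that are unable to complete all aspects of the study".

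**The concern.** A detectable effect is a statement about observed outcomes. If the number entered is the number randomised, the statement holds only when nobody is lost. The non-fatal components of the primary outcome come from the C-SSRS interview, and E2.2 names medical and death records only for death by suicide. Someone who stops attending therefore mostly stops contributing outcome data. Multiple imputation keeps that person in the analysis but does not replace the missing information.

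The .47 figure raises a separate question, because it can be checked from the formula and inputs printed beside it.

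What is at stake is how a null result is read. The trial is presented as fully powered, and its figures sit right at the earlier TMS effects it cites. A reader who takes .47 to .50 at face value would conclude more from a null result than the design supports.

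**Working it through.** **Inputs.** n = 65 per group, r = .2 and both formulas are from E2.2.1. Lehr's constant of 16 corresponds to about 80% power at two-sided 5%. The final significance level of 0.049 is from E2.1. Loss rates are my assumption, since the documents give none.

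**Step 1: the plan's figures with no loss.**
- Unadjusted: sqrt(16/65) = 0.496. The stated 0.50 reproduces.
- With r = .2: sqrt(16 × 0.96/65) = sqrt(15.36/65) = 0.486. The stated .47 does not reproduce.
- The exact constant in place of 16 gives 0.482 (0.483 at a level of 0.049). Using (1 − r) in place of (1 − r²) gives 0.444. One-sided testing gives about 0.43. None of these is .47.
- Solving for r at d = .47: r = sqrt(1 − 0.47² × 65/16) = 0.32. With r = .3 the formula gives 0.473.
- Solving for n at r = .2: 15.36/0.47² = 69.5, so about 70 per group.

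**Step 2: margin for loss on one comparison.**
- Unadjusted, d = 0.50 needs 16/0.25 = 64 observed per group. Tolerable loss is 1 − 64/65 = 1.5%.
- With r = .2 it needs 15.36/0.25 = 61.4. Tolerable loss is 1 − 61.4/65 = 5.5%.

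**Step 3: detectable d over an assumed range of loss, single time point.**

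| Loss | Observed per group | d, unadjusted | d, r = .2 |
|---|---|---|---|
| 0% | 65 | 0.50 | 0.49 |
| 10% | 58.5 | 0.52 | 0.51 |
| 20% | 52 | 0.55 | 0.54 |
| 30% | 45.5 | 0.59 | 0.58 |

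Power for d = 0.50 (two-sided 5%, t-based) at 0, 10, 20 and 30% loss is 81, 76, 71 and 66% unadjusted, and 82, 78, 73 and 67% with r = .2.

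**Step 4: if the test averages over 3, 6 and 12 months.** With correlation ρ between follow-ups (assumed .3 to .7) and baseline r = .2, the factor (1 − r²) becomes (1 + 2ρ)/3 − r². At 20% loss, treated as missing all three visits:
- ρ = .3: sqrt(16 × 0.493/52) = 0.39
- ρ = .7: sqrt(16 × 0.76/52) = 0.48

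Under that reading 0.50 survives 20% loss.

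**The case against.** The strongest reply is that a missing loss rate is not proof of a shortfall. A reader might infer that the trial is underpowered for d = 0.50 at any realistic loss. The documents do not support that. No rate is stated, the planned analysis adjusts for baseline, and with r = .2 the 0.50 figure still holds at 5% loss (0.499). At 10% loss, power is about 78% for d = .50 and 81% for d = .52. The shortfall becomes material only at about 20% loss or more.

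The second reply is that the primary model uses three follow-ups, while the formulas describe one comparison. This stands in part. If the tested group effect is an average over visits, the gain in Step 4 may cover the loss completely. But E2.2 includes treatment-by-time terms and names an immediate benefit as its main hypothesis. On that reading the averaging gain is not available, and the relevant loss is that at the 3-month endpoint, which may be lower than at 12 months. E2.2.1 does not claim any gain from repeated measures.

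The third reply is that 0.50 is worded for baseline, when nobody has dropped out. No treatment effect exists at baseline, so this is a wording fault to correct and no defence of the figure.

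Two further inferences should be resisted. One is that .47 is wrong because of dropout: it is wrong with everyone observed. The other is that the Cox power figure also ignores loss: it came from simulations whose censoring assumptions are not shown, so this cannot be told.

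Nothing here rescues .47 or supplies a loss allowance.

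**Conclusion.** The point holds in two parts of different strength.

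The .47 figure is an arithmetic error that needs no assumption. The plan's formula and inputs give 0.486. The difference is small, but the printed value overstates what 65 per group can detect.

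The absence of a loss allowance for the treatment aim is a gap in the assumptions. The figure of 0.50 is correctly computed for 65 observed per group and has almost no margin: about 1.5% loss unadjusted or 5.5% at r = .2. Beyond that its size is conditional: small at 5 to 10% loss, and a detectable d of 0.54 to 0.59 at 20 to 30%. These values assume a single time point, r of 0 or .2, and loss rates that are mine. The claim that the design fails to deliver 0.50 goes further than the documents allow. The paragraph should be corrected before results are known; the design need not change.

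**What to change.** Rewrite the primary-outcome part of E2.2.1, with no added enrolment:

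1. Change .47 to .49, or justify a baseline correlation of about .3.
2. Replace the reference to baseline with the follow-up time point at which the treatment effect is tested.
3. State an assumed range of loss at that time point and give the detectable d across it. For 0, 10, 20 and 30%: 0.50, 0.52, 0.55 and 0.59 unadjusted; 0.49, 0.51, 0.54 and 0.58 with r = .2.
4. Say that these are single-time-point figures, and that a test averaging over 3, 6 and 12 months would recover some or all of the loss.

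Carry the same range into the 0.5 SD statement in E2.3.1. For the Cox figure, state what loss or censoring the simulation assumed, and rerun it with loss only if none was included.

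The cost is one rewritten paragraph, a sentence in E2.3.1, a sentence on the Cox simulation and possibly one rerun. The stated figures become slightly less favourable.

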We will conduct 1 interim analysis and assess our primary aim when we have enrolled 32 persons per treatment group (~50% enrollment). The analyst and investigators will be blinded to treatment assignment in the interim analysis. We will test our a priori hypotheses and suggest consideration of early stopping to the DSMB if either group shows an effect on the primary outcome using O'Brien-Fleming stopping bounds [45] (i.e., a significance level of 0.0054). We will retain a significance level of 0.049 for our primary hypothesis at project completion.

E2.2 Primary hypothesis

We hypothesize that compared to sham TMS+BCBT, Veterans receiving active TMS+BCBT will demonstrate superior improvements in suicidal ideation and fewer suicide attempts. Our primary outcome for this aim is a composite measure of suicide behavior based on occurrence of any of five types of suicidal behavior: death by suicide, suicide attempt, interrupted or aborted attempts, and suicide preparatory acts. This composite score is derived from the Columbia Suicide Severity Rating Scale (C-SSRS). The C-SSRS captures data on number of attempts, aborted attempts, and interrupted attempts. Number of suicide behaviors will be added across these categories to yield a total suicide events score. Death by suicide will be captured by review of medical records and death records. The main exposure variable of interest is the random treatment assignment. Our analytic approach will be an ANCOVA-type mixed effect regression model [72]. This means the outcome composite measure at follow-up time points (e.g., 3, 6, 12 months) will be regressed on baseline value of the outcome, design factors, and treatment assignment, dummy variables for time (baseline as reference) and interactions of treatment assignment and time dummies. Random intercepts and exchangeable error covariance structure will accommodate non-independence of observations owing to the repeated measures design.

The main effect of TMS as adjunctive to BCBT will be tested with the main effect of group assignment to the joint intervention condition. The time effect interactions of TMS assignment test hypotheses about the maintenance of gains at 3, 6 and 12 months. Our main hypothesis is that there is an immediate beneficial effect of TMS exposure. For our secondary outcome, (time to first suicide attempt over 12 months) we will use a Cox proportional hazards model analysis framework.

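### The baseline-adjusted detectable effect for the primary outcome (section E2.2.1) does not follow from its own formula: r = .2 with 65 per group gives d = .49, not .47

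*Combined protocol and SAP*

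**What the plan says.** Section E1 (Design and Sample Size) plans to randomize 130 Veterans, about 65 to each arm. Section E2.2.1 then states two minimum detectable effects for the primary outcome, both from Lehr's rule with n as the per-group size:

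- **Unadjusted:** sqrt(16/n), "or 0.50 standard deviation units, a medium effect size".
- **Baseline-adjusted:** d = sqrt(16(1 − r²)/n), where r is the pre-post correlation of the composite. Here "under the assumption of a moderate correlation (r = .2) the minimum detectable effect size is" d = .47.

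The paragraph gives no other n, no attrition allowance and no second value of r for this calculation. It does not state the power or alpha behind the constant 16 for the primary outcome. Section E2.1 sets the final significance level: "We will retain a significance level of 0.049 for our primary hypothesis at project completion".

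**The concern.** The formula, both of its inputs and its result stand in the same sentence, so a reader can check it directly, and it does not reproduce. The adjusted figure is the more favourable of the two and is the plan's stated gain from using ANCOVA. From the unadjusted .496, the formula at r = .2 allows a fall of .010, to .486. The printed .47 implies a fall of .026. The benefit credited to baseline adjustment is therefore more than twice what the stated correlation supports.

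What is at stake is the accuracy of the power statement for the primary outcome. A reader cannot tell from the text whether the investigators expect a correlation of .2 or one nearer .3.

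**Working it through.** **Inputs.** n = 65 per group (E1 and E2.2.1), r = .2 (E2.2.1), and the formula d = sqrt(16(1 − r²)/n) (E2.2.1).

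**1. The plan's unadjusted figure.** sqrt(16/65) = sqrt(0.24615) = .496, which rounds to the stated 0.50. So n = 65 and the constant 16 are being read as the plan intends.

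**2. The plan's adjusted figure.** sqrt(16 × (1 − 0.04)/65) = sqrt(15.36/65) = sqrt(0.23631) = .486, which rounds to .49. The plan prints .47. Difference: .486 − .470 = .016 SD.

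**3. Can rounding explain it?**
- Any r that rounds to .2 (.15 to .25) gives d from .491 down to .480.
- Starting from the rounded 0.50: 0.50 × sqrt(0.96) = .490.

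**4. Can another method explain it?** At n = 65 and r = .2:

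| Variant | d |
|---|---|
| Exact normal multiplier, two-sided .05, 80% power | .4815 |
| Exact normal multiplier, two-sided .049, 80% power | .4830 |
| Noncentral t, two-sided .05, 80% power | .485 |
| Two-sided .05, 90% power | .557 |
| One-sided .05, 80% power | .427 |
| One-sided .05, 90% power | .503 |
| Factor (1 − r) in place of (1 − r²), constant 16 | .444 |
| Change-score factor 2(1 − r), constant 16 | .628 |

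None rounds to .47.

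**5. What would give .47?**
- Solving for r at n = 65: r = sqrt(1 − d² × 65/16). For d = .475, r = .289. For d = .465, r = .349. Exactly .47 needs r = .320, and r = .30 gives sqrt(16 × 0.91/65) = .473.
- Solving for n at r = .2: 15.36/.47² = 69.5, so 70 per group.

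Since n = 65 is stated in two sections and reproduces the unadjusted figure, the error lies in r or in d.

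**6. Size in terms of power.** 65 per group, r = .2, residual SD sqrt(0.96), two-sided alpha .05 (assumed):

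| Method | d = .47 | d = .486 |
|---|---|---|
| Normal approximation | 78.1% | 80.7% |
| Noncentral t (127 df) | 77.5% | 80.1% |

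The gap is about 2.6 percentage points by either method. At the final alpha of .049, noncentral t gives 77.2% at d = .47. At d = .50 with r = .2, it gives 82.3% (alpha .05) or 82.1% (alpha .049).

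**The case against.** The strongest reply is that nothing rests on .47. The 130 is stated in E1 and is not derived from it. The effect carried forward to the secondary outcomes in E2.3.1 is the unadjusted 0.5 SD, which is correct. Lehr's rule is itself approximate, and the slip is about 3% of the effect. All of this stands, and it is why the point is minor. It does not make the printed figure right.

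A second reply is that the planned model may do better than the formula. Section E1.1 adjusts for the urn balancing factors as well as the baseline value, and section D4.4.1b lists number of previous attempts among those factors. In the formula, .47 needs an explained share of variance of .083 to .122 in place of r² = .04. The extra covariates might supply that, but E2.2.1 attributes the gain to the pre-post correlation alone and states it as .2. So this does not rescue the figure. It does mean that the slip is no evidence that the planned analysis is weaker than the plan claims.

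A reader might also infer more than the documents support:

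- **That the detectable effect should be restated as a rate ratio**, because the primary outcome is a count: "Number of suicide behaviors will be added across these categories to yield a total suicide events score". The planned primary model is an ANCOVA-type mixed regression on that score, for which a standardized difference is a natural measure. The documents give no event rate or dispersion from which to derive a ratio.
- **That d of about .5 is a very large fall in suicidal events**, by analogy with the attempt risks of 21% and 4.5% in the same section. Those concern a binary 12-month attempt outcome and do not carry over to a summed score of unknown SD.
- **That the remark on minimal clinical significance must be deleted.** It rests on a cited source that cannot be checked here, and the arithmetic does not bear on it.
- **That preparatory acts are left out of the score.** E2.2 lists them among the behaviours in the composite and sums across those categories.

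**Conclusion.** The point holds, as a minor one: the figure is wrong as written. With the plan's own formula, n and r, the baseline-adjusted detectable effect is .486 (d = .49), not .47. This needs nothing outside E2.2.1.

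The documents do not show which number is the misprint. A correlation of about .3 would fit .47, but that is an inference. The power figures rest on a two-sided alpha of .05 and, for the comparison with 80%, on the usual reading of Lehr's constant; E2.2.1 states neither for the primary outcome.

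It would be wrong to conclude that the trial is underpowered or that 130 must change: power at d = .50 with r = .2 is above 80%, and .49 is as much a medium effect as .47.

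**What to change.** Reconcile r and d in section E2.2.1, in one of two ways:

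- keep r = .2 and write *d = .49 (r = .2)*; or
- correct r to about .3, state the justification for that correlation, and keep d = .47.

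This changes one figure, or one figure and a sentence of justification. Sample size, visits and analysis stay as they are. The only cost is a slightly less favourable stated effect if r = .2 stands.

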E2.3.1 Statistical power and sample size considerations: Sample size considerations for part

(a) are similar to the primary hypothesis, and the minimum detectable effect size difference is a standardized mean difference of 0.5SD units. Without pilot data on the number of hospitalizations/crisis visits, it is difficult to forecast the distribution and detectable difference in distribution on the count outcome (part b). Rules of thumb provided by Van Belle [77] suggest we will be able to detect a relative rate of $\exp(4/\sqrt{n})$, where n is the per-group sample size, or a reduction in the rate of hospitalizations of about 61% or more among those receiving active TMS+BCBT plus versus sham.

E2.4 Moderator and mediator effects

In addition to the above hypotheses, we will conduct exploratory latent growth curve analyses to compare the trajectory of change for primary, secondary, and tertiary outcomes (i.e. linear ascending, descending, or quadratic) between sham TMS+BCBT versus active TMS+BCBT. We will include moderator variables in these models (e.g. diagnosis, comorbidity, gender), which may identify patients who will benefit more or less to the addition of active TMS+BCBT versus sham TMS+BCBT. We also will investigate mediating variables to determine the mechanisms through which TMS produces its effects on clinical outcomes. The set of analyses in this aim are motivated by [78], who suggest exploratory, hypothesis generating analyses be conducted after primary study aims are addressed to attempt to decide for which sample sub-groups the intervention might be more efficacious or have more lasting effects. The analytic approach will be like that described for the primary and secondary aims, although in addition to the timepoint effect indicators, we will examine models with more parsimonious time structure (e.g., linear, piecewise linear, negative exponential) and then attempt to describe factors that predict variations in important components of the implied change trajectory. We will make use of generalized linear mixed effect models and compare alternative time bases using information criteria before adding covariates, mediators, and moderators. Treatment effect mediation will be evaluated by comparing treatment effects estimated before and after adjusting for the main effect of putative mediators. Moderation effects will be examined as three-way interactions of the putative moderator, treatment assignment, and time.

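### The detectable rate for hospitalisations/crisis visits is printed as a 61% reduction when its rule gives 39%, and the rule leaves out the event rate and overdispersion on which the planned negative binomial test depends

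*Combined protocol and SAP*

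**What the plan says.** Section E2.3 lists the number of psychiatric hospitalisations/crisis visits as secondary outcome (b) and fixes its analysis: "the outcome will be a count variable, for which we will use negative binomial regression".

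Section E2.3.1 gives the sensitivity for that outcome. It begins with a caveat, "Without pilot data on the number of hospitalizations/crisis visits, it is difficult to forecast the distribution", then says that rules of thumb "suggest we will be able to detect a relative rate of $\exp(4/\sqrt{n})$, where n is the per-group sample size", and translates the result as "a reduction in the rate of hospitalizations of about 61% or more among those receiving active TMS+BCBT plus versus sham".

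The group size comes from Section E1: "Approximately 65 will be randomized to active TMS+BCBT and 65 participants will be randomized to sham TMS+BCBT". No mean count, overdispersion, alpha, power or length of counting period is stated for this outcome.

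**The concern.** There are two faults in one sentence. First, the rule's output at 65 per group is a rate ratio of 0.61, and the plan reports the ratio as if it were the reduction.

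Second, repairing the percentage would leave a 39% reduction that still does not belong to the planned test. The rule has the same form as the rule for means in Section E2.2.1, the square root of 16/n, with a standard deviation of 1 assumed on the log scale. A negative binomial comparison has no fixed standard deviation of 1: its variance depends on how often events occur and how unevenly they are spread across Veterans.

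At stake is how a non-significant result on a named secondary hypothesis would be read. If the plan said that a 39% reduction was detectable, such a result could be taken as evidence against a reduction that the trial may have had little chance of finding.

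**Working it through.** **Inputs.** n = 65 per group (Section E1). The rule exp(4/√n) (Section E2.3.1). Negative binomial regression (Section E2.3). Two-sided 5% and 80% power are assumed, since none is stated here; Section E2.2.1 uses 5% and 81.1% for time to first attempt. The sham mean count mu0 and overdispersion k are assumptions, because the documents give neither.

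**Step 1: the plan's figure.** 4/√65 = 0.496; exp(0.496) = 1.64; 1/1.64 = 0.609. The reduction is 1 − 0.609 = 39%. The number 61 is reproduced only as the remaining ratio. A true 61% reduction from this rule would need about 18 per group.

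**Step 2: the variance of the planned test.** For two equal arms with mu1 = mu0 × RR,

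Var(log RR) = (1/mu0 + 1/mu1 + 2k)/n,

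power ≈ Φ(|log RR|/SE − 1.96).

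**Step 3: what the rule requires.** For 80% power the effect must equal 2.80 SE, so 1/mu0 + 1/mu1 + 2k may be at most 65 × 0.496² / 2.80² = 2.04. Hence (1/mean + k), averaged over the arms, must be about 1.02 or less. With RR = 0.609, 1/mu0 + 1/mu1 = 2.64/mu0, which gives the smallest sham mean for 80% power:

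- k = 0: 2.64/2.04 ≈ 1.30
- k = 0.5: 2.64/1.04 ≈ 2.54
- k = 1: about 69 events per person, in practice not reachable
- k = 2: no solution

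As the mean grows without limit, SE tends to √(2k/65). For k = 1, 0.496/0.1754 − 1.96 = 0.868, so power is capped at 80.7%. For k = 2, 0.496/0.2481 − 1.96 = 0.040, so it is capped at 51.6%. These two caps need no assumed event rate.

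**Step 4: unadjusted power over an assumed grid (k = 0.5 / 1 / 2).**

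| Sham mean | Ratio 0.61 (39% reduction) | Ratio 0.39 (printed 61% reduction) |
|---|---|---|
| 0.5 | 36 / 32 / 26% | 76 / 71 / 62% |
| 1 | 55 / 46 / 34% | 94 / 90 / 79% |
| 2 | 75 / 59 / 41% | over 99 / 97 / 88% |

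Worked cell: mean 1, k = 1, ratio 0.609. SE = √((1 + 1.642 + 2)/65) = 0.267; 0.496/0.267 − 1.96 = −0.10; power 46%. Simulating the likelihood-ratio test (1,000 runs) gave 45%.

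**Step 5: ratios detectable with 80% power (k = 0.5 / 1 / 2).**

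- sham mean 0.5: 0.36 / 0.33 / 0.29
- sham mean 1: 0.50 / 0.45 / 0.38
- sham mean 2: 0.59 / 0.52 / 0.44

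The formula is slightly conservative at low means. At mean 0.5 and k = 2, a likelihood-ratio simulation (1,500 runs) gave 85% power at a ratio of 0.28 and 77% at 0.32, which puts the 80% point nearer 0.31 than 0.29.

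**The case against.** Five fair points can be made for the plan.

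- **The plan discloses the weakness.** It says that it lacks pilot data and presents the figure as a rule of thumb. The outcome is secondary. This stands and limits the importance of the point, but a single detectable effect is still stated.
- **The sentence as printed is roughly achievable.** A reader might infer that the trial is badly underpowered for the effect that the plan names. The documents do not support that: the printed effect is a 61% reduction, and the ratio 0.39 has about 62-99% power over the grid. Low power concerns the 39% reduction that would appear once the percentage is corrected.
- **The grid has no anchor in the documents.** A reader might also infer that 0.61 is undetectable in most plausible cases. That cannot be claimed without a mean or k. With a sham mean of 2 and k = 0, power for 0.61 is 94%; with a mean of 5 and k = 0.5 it is 90%. The outcome pools hospitalisations with crisis visits in Veterans enrolled soon after a crisis (Section D2.1), over a counting period that is not fixed, so means above 2 cannot be excluded.
- **Adjustment may help.** Section E1.1 adjusts the main analysis for the baseline value of the outcome and the balancing factors. If this applies here and prior use predicts later use, the residual k would be lower than the unadjusted k used above.
- **Baseline chart data could mislead.** The 12 months before enrolment can include the crisis that led to enrolment, which would probably overstate the mean and hence the power. This stands and shapes the fix.

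None of these points supplies the missing variance term.

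**Conclusion.** The concern holds in a limited form. That 0.61 is a ratio and not a reduction is certain and needs no assumption. So is the fact that the rule omits the mean count and overdispersion that govern the planned test. It follows that replacing 61% by 39% would not repair the sentence: a 39% reduction is detectable with 80% power only if events are frequent and overdispersion is low.

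The size of the shortfall rests on assumed means and k, an unadjusted comparison, two-sided 5% and no dropout. Within those assumptions, power for 0.61 lies anywhere from 26% to 75%. This is a minor correction to a stated sensitivity. It does not challenge the sample size or the choice of negative binomial regression.

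**What to change.** In Section E2.3.1, delete both the exp(4/√n) claim and the 61% wording. In their place, state the counting period, the assumed sham means and values of k, and the rate ratio detectable with 80% power, two-sided 5% and 65 per group, from the negative binomial formula or by simulation. Section E2.2.1 already works this way for time to first attempt, with an assumed event rate and simulation.

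Suggested content: for sham means of 0.5 to 2 and k of 0.5 to 2, the detectable rate ratio runs from about 0.29 (mean 0.5, k = 2) to 0.59 (mean 2, k = 0.5). Add that the formula is slightly conservative at low means and that adjustment for prior utilisation may lower k.

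The chart extraction in Section D5, which covers the current month and the 12 before it, could inform the mean and k, provided that the index episode is excluded.

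The cost is a short calculation and a few reworded sentences, with no extra patients. The drawback is that one figure becomes a range that depends on stated assumptions.
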